12.2.2. Control of Systematic Error/Bias

To reduce selection bias in this non-randomized study, each study center will be permitted to enroll subjects in only one of the treatment groups. Physicians will be selected based on device and clinical research experience and the decision as to which device to implant in subjects prior to study initiation at each center. Some study centers may be permitted per Boston Scientific to enroll subjects in both treatment and control groups. All decisions will be documented prior to subject enrollment. All subjects meeting the eligibility criteria at the study center will be screened and enrolled as applicable.

Propensity score stratification will be utilized to address the potential imbalance in risk factors between groups, described in Section 12.2.3 (Propensity Score Methodology). This analysis will be performed blind to all clinical outcome data and prior to performing any analysis of endpoints.

12.2.3. Propensity Score Methodology

Analyses comparing the treatment groups will be adjusted for the propensity score. The propensity score is the probability that the subject enrolled in the mesh arm rather than the native tissue (control) arm, given the characteristics of the subject and center. The characteristics identified are as follows: age, race, body mass index, smoking, diabetes, post-menopausal, prior prolapse repair, prior hysterectomy, estrogen use, POP-Q C measurement, POP-Q Ba measurement, POP-Q Bp measurement, concomitant repair for stress urinary incontinence, and surgeon case volume. Logistic regression of both treatment arms (i.e., (transvaginal mesh repair vs. native tissue repair) on these characteristics will be used to estimate the propensity score. The subjects will then be partitioned into five strata

corresponding to quintiles of the propensity score. If the balance between treatment arms within the strata is deemed adequate, the treatment difference adjusted for propensity score stratum will be estimated as described in the following.

The propensity adjusted treatment difference will be based on averaging the treatment differences of the propensity score strata. For a binary outcome, the within-stratum treatment difference is $D_j = p_{Tj} - p_{Cj}$, where p_{Tj} and p_{Cj} is the proportion of treatment and control subjects, respectively, in stratum j . The variance of D_j is approximately

$$V_j = \frac{p_{Tj}(1 - p_{Tj})}{n_{Tj}} + \frac{p_{Cj}(1 - p_{Cj})}{n_{Cj}}$$

Denoting the number of subjects in stratum j by $n_j = n_{Tj} + n_{Cj}$, the treatment difference will be estimated by the (weighted) mean of the within-stratum treatment differences

$$D = \sum_j \frac{n_j}{n} D_j$$

where $n = \sum_j n_j$ is the total sample size across all strata and study arms. D is approximately normally distributed with variance

$$V = \sum_j \left(\frac{n_j}{n}\right)^2 V_j$$

from which a confidence interval for the true treatment difference will be constructed. For each continuous outcome, the confidence interval will be constructed similarly, with D and V obtained as above with the treatment difference within each stratum replaced by $D_j = \bar{X}_{Tj} - \bar{X}_{Cj}$, where \bar{X}_{Tj} and \bar{X}_{Cj} , respectively, is the mean of the treatment and control subjects, and

$$V_j = \frac{S_{Tj}^2}{n_{Tj}} + \frac{S_{Cj}^2}{n_{Cj}}$$

where S_{Tj}^2 and S_{Cj}^2 are the variances of the treatment and control subjects in stratum j .

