7.1. Primary Endpoints

The primary endpoint of the study is to achieve superiority of mesh over native tissue repair at 36 months as compared to baseline.

Success will be based on a composite of objective and subjective measures, and subjects will be considered a surgical success if each of the three criteria is met:

1. Objective success is achieved by the subject having an anatomic outcome defined as the leading edge of prolapse at or above the hymen in the operated compartment:
 - Anterior segment: Leading edge of anterior prolapse is at or above the hymen or POP-Q point Ba \leq 0.

- Apical segment: The vaginal apex does not descend more than one-half into the vaginal canal (i.e. POP-Q point C < -1/2 TVL) for multi-compartment prolapse or POPQ point C ≤ 0 for single compartment apical prolapse.
2. Subjective success is achieved if the patient denies symptoms of vaginal bulging per PFDI-20 question 3, answering “no” or “yes” but “Not at all” bothersome (<2).
 3. No retreatment for POP: no additional surgical treatment for POP in the segment(s) of the vagina treated at the index surgery or no pessary use since index surgery (i.e., ‘treated segment’ refer to the target compartment).

Additionally, a co-primary endpoint of the study is to achieve non-inferiority of mesh to native tissue repair for safety by comparing rates of serious device or serious procedure complications between baseline and the 36 month time point. Serious injury is defined per 21 CFR 803.3, i.e., life threatening, results in permanent impairment of a body function or permanent damage to a body structure, or injury or illness that requires medical or surgical intervention to preclude impairment of a body function or permanent damage to a body structure.

7.2. *Secondary Endpoints*

The secondary endpoints of the study include assessments of complications and subject reported outcomes:

1. Incidence of mesh erosion
2. Incidence of mesh exposure
3. Incidence of de novo dyspareunia
4. Improvement in subject-related outcomes at 36 months compared to Baseline ((pelvic floor symptoms (PFDI-20), QOL (PFIQ-7), sexual functioning (PISQ-12) TOMUS pain scale)
5. Assessment of subject’s level of improvement, measured by the Patient Global Impression of Improvement for Prolapse (PGI-I for Prolapse)
6. Absence of re-intervention and re-surgery for recurrence of POP, persistence of disease, or mesh exposure/erosion
7. Surgical success based on the following composite outcome:

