8.1. Scale and Duration

The study will be conducted at up to 40 sites at a rate of approximately 1-2 subjects per month. Sites will be encouraged to enroll a minimum of 10 subjects and up to a maximum of 50 subjects.

It is anticipated that approximately 414 subjects will be enrolled in total to achieve 330 subjects (165 subjects per treatment arm) for the co-primary endpoint analysis at 36 months post-surgery to achieve non-inferiority of mesh to native tissue repair for safety by comparing rates of serious procedure-related and device-related complications between baseline and the 36 month time point. Due to the partnership with the PFD Registry, it is anticipated a portion of the control arm subjects will be shared from the Registry.

The enrollment period is expected to be approximately 12 to 18 months after the final study center has been permitted to enroll subjects. A potential 20% “lost to follow-up” rate is anticipated.

Once enrolled into the study, subjects will be followed to 36 months post-surgery to be evaluated for the primary endpoint analysis. The total duration of each subject’s participation in the study is 36 months from time of procedure.

Subjects who undergo a medical intervention (surgical or non-surgical) to treat recurrence, persistence of POP, or a mesh or suture complication will be followed to 36 months, post the initial study procedure.

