12.1.1.2. Sample Size

The statistical power calculation is based on a superiority assumption with a binary primary outcome. Success, based on a composite endpoint of anatomic and symptomatic success at 36 month is assumed to be 70.0% for the native tissue arm and 85.0% for transvaginal mesh arm.¹⁷⁻²¹ With 2-sided type I error of 0.05 and type II error of 0.1 (power 90%), 316 subjects (158 subjects per arm) are needed to detect 15% difference of transvaginal mesh to native tissue repair. In addition to a superiority assumption, statistical testing will be performed for non-inferiority using a margin of -12%.

To assess for safety, the overall complication rate (i.e. serious adverse device effects and serious procedure-related adverse events) is anticipated to be approximately 14%.²² With type I error of 0.05 and type II error of 0.20 (power 80%), 298 subjects (149 subjects per arm) are needed to detect non-inferiority with a margin of 10%.

To assess for office-based interventions for complications, the rate is anticipated to be approximately 2%.²² With type I error of 0.025 and type II error of 0.10 (power 90%), 330 subjects (165 subjects per arm) are needed to detect non-inferiority with a margin of 5%.

To assess for of surgical intervention for complications, the rate is anticipated to be approximately 1%.²² With type I error of 0.025 and type II error of 0.10 (power 90%), 260 subjects (130 subjects per arm) are needed to detect non-inferiority with a margin of 4%.

Non-surgical subjects will be enrolled by the PFD Registry and analyzed in this clinical study. Non-surgical subjects will not be enrolled into this clinical study. Using the above calculations and assuming a 20% loss to follow-up rate, a total of 414 subjects (207 per study arm) will be enrolled to achieve the primary endpoint of success at 36 months.

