12.3.5.4. Subjects with surgical intervention for recurrence or complications

Each of device-related or procedure-related adverse events during the period after the re-surgery will be summarized by the vaginal compartment(s) (i.e. apical only, anterior only, apical and anterior) treated in the index procedure within each treatment group.

12.3.6. **Additional Data Analyses**

- Assessment of EQ-5D score for health status at 12, 24 and 36 month as compared to baseline
- Assessment of SSQ-8 score for surgical satisfaction at 6, 12, 24 and 36 month

Propensity score adjusted confidence intervals described in Section 12.2.3 (Propensity Score Methodology) will be used to summarize EQ-5D and SSQ-8 score improvements between two groups.

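### Baseline compartment class sets the anatomic success threshold but is absent from the propensity model, which can leave residual bias of unknown direction and conditional size

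*Combined protocol and SAP*

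**What the plan says.** Section 7.1 makes anatomic success depend on class. The anterior segment needs Ba ≤ 0. The apical segment has two rules: the stricter one reads "i.e. POP-Q point C < -1/2 TVL) for multi-compartment prolapse or POPQ point C", and the text is completed by "for multi-compartment prolapse or POPQ point C ≤ 0 for single compartment apical prolapse". Success is judged in the compartment operated on. The section does not say whether multi-compartment status comes from the baseline examination or from the surgery.

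Section 9.2, criterion 3, defines class at entry: anterior alone if Ba ≥ 0, apical alone if C ≥ 0, and multi-compartment if C ≥ -1/2 TVL together with Ba ≥ 0. Vaginal length is measured at baseline (section 11.4.2).

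Section 12.2.3 lists the propensity covariates. The anatomic ones are "POP-Q C measurement, POP-Q Ba measurement, POP-Q Bp measurement"; neither class nor TVL is listed. Women are split into five quintile strata, and stratum differences are averaged with weights n_j/n. The adjusted estimate is conditional on adequate balance within strata, but no covariates, metric, limit or fallback are named. Section 12.1.1.3 rests the superiority decision on the resulting 95% interval.

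The only planned summary by compartment is in section 12.3.5.4. It covers adverse events after re-surgery, grouped by the compartments ("i.e. apical only, anterior only, apical and anterior) treated in the index procedure within each treatment group").

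**The concern.** Class affects the outcome through the definition of success itself, and it is a step function of the POP-Q values. C and Ba as plain measurements do not fully stand in for it. Two examples, with illustrative TVL values:

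- Two women both have C = -4 and Ba = +1. With TVL 9 the cut is -4.5, so the first is multi-compartment and must reach C < -4.5. With TVL 7 the cut is -3.5, so the second is anterior only and needs Ba ≤ 0. Their C and Ba are identical but their success rules differ.
- Two women both have C = +1. With Ba = -1 the first is apical only and succeeds at C ≤ 0. With Ba = 0 and TVL 9 the second must reach C < -4.5. A 1 cm difference in Ba moves the apical threshold by 4.5 cm.

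The arms are not randomized. If they differ in class beyond what C and Ba explain, part of that difference stays inside the quintiles and enters the confirmatory contrast. More multi-compartment women in the mesh arm would cost power; more in the control arm would favour a false superiority finding.

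**Working it through.** **The plan's own figures.** Section 12.1.1.2 gives success "assumed to be 70.0% for the native tissue arm and 85.0% for transvaginal mesh arm" and "With 2-sided type I error of 0.05 and type II error of 0.1 (power 90%), 316 subjects (158 subjects per arm". The unpooled two-proportion formula gives n = (1.960 + 1.282)² × (0.70×0.30 + 0.85×0.15) / 0.15² = 158 per arm, as stated. Section 8.1 plans "414 subjects will be enrolled in total to achieve 330 subjects (165 subjects per treatment arm", and 165/0.80 = 206.25, rounded up to 207 per arm, matches the enrolment target in 12.1.1.2 ("assuming a 20% loss to follow-up rate, a total of 414 subjects (207 per study arm) will be enrolled").

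**Bias without adjustment.** Bias = (arm difference in multi-compartment share) × (success gap by class). Neither factor is in the documents. Assuming 0.19 and 0.15 to 0.25, it is 0.19×0.15 = 2.9 points to 0.19×0.25 = 4.8 points.

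**Bias left by the planned score.** This needs simulation. Assumed inputs: 414 women, TVL mean 9 (SD 1), C mean -3 (SD 4), Ba mean 1.5 (SD 2), class by criterion 3 (about 60% multi-compartment, about 5% apical only), success 15 to 25 points lower in multi-compartment women. The score is linear in C and Ba, with five quintiles and n_j/n weights as in 12.2.3. The class imbalance is about 18 points. Entries are absolute bias in percentage points.

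| How arm selection works | Planned score | Class added |
|---|---|---|
| Through C only | about 0.1 | 0.1 to 0.2 |
| Mixed | 0.6 to 1.0 | 0.2 to 0.35 |
| Directly on class | 1.3 to 2.1 | 0.2 to 0.4 |

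A run of the direct case with a 19-point imbalance gave 1.4 to 2.3 under the planned score.

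**Second set of inputs.** Rounded values, Ba mean 2 (SD 2), C mean -3 (SD 3.5), TVL mean 9 (SD 1), success gap 10 to 20 points. With direct selection and an imbalance of 11 to 32 points, the planned score leaves 0.4 to 2.5 points, adding TVL leaves 0.4 to 2.4, and adding class leaves 0.2 to 1.3. With selection through C, the planned score leaves 0.1 to 0.3 and adding class changes nothing.

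**Effect on power (bias against mesh).** SE = √(0.85×0.15/158 + 0.70×0.30/158) = 0.0462, and power = Φ((0.15 - b)/SE - 1.96):

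- b = 0: 0.90
- b = 0.001: 0.90
- b = 0.0135: 0.84
- b = 0.021: 0.80
- b = 0.0229: 0.79

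**Effect on false superiority (bias towards mesh).** Taking 70% in both arms, SE = √(2×0.21/158) = 0.0516, and the error rate = 1 - Φ(1.96 - b/SE):

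- b = 0: 2.5%
- b = 0.0135: 4.5%
- b = 0.021: 6.0%
- b = 0.0229: 6.5%

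**The case against.** Much of the case against stands. Class is determined by Ba, C and TVL, and Ba and C are already in the score. If the arms differ in class only because they differ in apical descent, the plan already removes nearly all of the bias. Section 12.2.3 also does not require linear terms; the simulations assume them. Its balance check, done blind to outcomes (section 12.2.2), could reveal a class imbalance.

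Three stronger readings are tempting, and the documents do not support them.

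- A reader might infer that mesh and control women will probably differ in class, because the device gives apical support (section 4) while control may be colporrhaphy alone (section 8.2.1). Those passages describe operations, not baseline anatomy. Arm is set mainly by centre before enrolment (sections 8.2 and 12.2.2), so imbalance is possible but not shown.
- A reader might infer that adding class reliably recovers 6 to 11 points of power. That holds only if selection acts directly on class. If it runs through C, the gain is about zero.
- A reader might blame the missing TVL. Adding TVL barely changes the residual bias (1.26 versus 1.31 points under the first set of inputs). What remains comes mainly from the cut-point form of class.

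The gap itself survives. The balance check neither names class nor sets a limit, so nothing in the plan requires class to be examined.

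**Conclusion.** The point holds as a conditional one. The endpoint rule depends on class, and the propensity model as listed does not ensure balance on class. Residual bias arises only if class differs by arm within quintiles and success differs by class; the documents give neither quantity, and the direction is unknown. Under the stated assumptions the residual runs from about 0.1 to about 2 points. The consequence is a loss of about 0 to 11 points from 90% power if mesh has more multi-compartment women, or false superiority of 2.5% to about 6.5% in the reverse case. The upper ends are the direct-selection scenario (2.3 points of bias), not an expected value.

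A related gap may matter more. If multi-compartment status in 7.1 is read from the surgery performed, the threshold can depend on treatment, and no baseline propensity score can correct that.

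**What to change.** 1. In 12.2.3, add baseline compartment class (anterior only, apical only, anterior and apical), derived from the pre-operative POP-Q by inclusion criterion 3, as a categorical covariate in the propensity logistic regression. Apical only may be sparse: about 5% under the assumed inputs, or about 0.05×414 = 21 women over two arms and five strata. Allow a multi-compartment versus single-compartment indicator if needed.
2. In the same section, name class in the within-quintile balance check and give a numerical limit, for example on the standardized difference.
3. In 7.1, state that this baseline class, and not the operation performed, sets the multi-compartment threshold.

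The cost is one or two model degrees of freedom and a slightly more separated score, using data already collected. The change should be fixed before any outcome analysis, as 12.2.2 requires of the propensity work. That includes the 12-month interim, which uses the same adjustment (section 12.3.8.2).

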Secondary Endpoints	
1. Incidence of mesh erosion2. Incidence of mesh exposure3. Incidence of de novo dyspareunia4. Improvement in subject specific outcomes at 36 months compared to Baseline (pelvic floor symptoms (PFDI-20), QOL (PFIQ-7), sexual functioning (PISQ-12), TOMUS pain scale5. Assessment of subject’s level of improvement, measured by the Patient Global Impression of Improvement for Prolapse (PGI-I for Prolapse)6. Absence of re-intervention or re-surgery for recurrence or persistence of POP or mesh exposure/erosion7. Surgical success based on the following composite outcome:
a. Subjective success: patient denies symptoms of vaginal bulging per PFDI-20 question 3, answering “no” or “yes” but “Not at all” bothersome (<2)b. Anatomic success (in the operated compartment):
• Anterior Segment: No anterior prolapse at or beyond the hymen or POP-Q point Ba<0• Apical Segment: The vaginal apex does not descend more than one-half into the vaginal canal (i.e. POP-Q point C < 1/2 TVL) for multi-compartment prolapse or POPQ point C < 0 for single compartment apical prolapsec. No retreatment for POP: No additional surgical treatment for POP in the segment(s) of the vagina treated at the index surgery or no pessary use since index surgery8. Device or procedure-related incidence of the following: pelvic pain, infection, vaginal shortening, atypical vaginal discharge, neuromuscular problems, vaginal scarring, de novo vaginal bleeding, fistula formation and/or de novo voiding dysfunction

Postmarket Study PS130044: A Prospective, Non-Randomized, Parallel Cohort, Multi-center Study of Uphold LITE vs. Native Tissue for the Treatment of Women with Anterior/Apical Pelvic Organ Prolapse	
Method of Assigning Subjects to Treatment	This study is a prospective, non-randomized, parallel cohort, multi-center study. Approximately 414 subjects will be enrolled and will either receive transvaginal mesh (treatment) or a native tissue repair (control) procedure. Study centers will either participate to enroll only mesh subjects or only native tissue subjects to reduce bias; or a combination of mesh and native tissue subjects depending on subject population and per Sponsor discretion.

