8.2. Treatment Assignment

This post-approval study is a prospective, non-randomized, parallel cohort study across multiple centers. Subjects will be screened against the study Inclusion/Exclusion criteria and if eligible, enrolled into the study after providing Informed Consent.

Study centers will be selected by Boston Scientific to perform the study procedure as either a treatment center or a control center, depending on experience to reduce selection bias. Some study centers may be selected to enroll a combination of treatment and control subjects, depending on subject population and per Boston Scientific discretion.

Treatment will occur after all Baseline procedures have been completed and the subject has been deemed eligible for the study. Baseline procedures may be combined with the screening visit and may occur within three months prior to the study procedure, with confirmation of no evidence of infection prior to the procedure. Due to the allowable window of up to three months between baseline and study procedure, the study staff will confirm that subjects are still electing to undergo the study surgery with confirmation of no evidence of infection.

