10.1. Point of Enrollment

Subjects will be considered enrolled in the study once an incision is made in the vaginal wall. All enrolled subjects will have been consented and assigned to receive either the treatment or control procedure per site assignment. All enrolled subjects with a surgery initiated (i.e. incision in vagina) will be considered part of the Intent-to-Treat (ITT) population for the final study analysis. All ITT subjects who undergo the assigned study procedure and had no major protocol deviations will be considered part of the Per Protocol analysis.

The following study timeline (see Table 10.1-1) is based on milestones completed and the current follow-up visit cadence.

Table 10.1-1: Study Timeline

Milestone	Date
Date of study initiation ¹	August 2013
Date of initiation of subject enrollment	October 2013
Date of enrollment completion	December 2016
Expected date of study follow-up completion	December 2019
Expected date of Final Report submission ²	June 2020

¹Study initiation is defined as the date the first study site is “enrollment ready” (i.e. IRB approved, fully executed contract)

²Assuming 6 months from last patient visit completion.

All efforts will be made by site staff to ensure minimal loss to follow-up of patients and will follow a site-specific loss to follow-up plan. These plans will include efforts such as telephone follow-up, Investigator-patient counseling, visit reminder tools, patient stipends if permitted per site budget, and/or other communication methods.

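### To the extent that center determines arm and within-center correlation remains after adjustment, the variance in 12.2.3 is too small and the co-primary and interim intervals are too narrow

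*Combined protocol and SAP*

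**What the plan says.** **How arm is tied to center.** Section 12.2.2 states that "each study center will be permitted to enroll subjects in only one of the treatment groups", and then makes an exception: "Some study centers may be permitted per Boston Scientific to enroll subjects in both treatment and control groups". Section 8.2 has the same default, "Study centers will be selected by Boston Scientific to perform the study procedure as either a treatment center or a control center", with combination centers allowed at the sponsor's discretion. The Synopsis says "Study centers will either participate to enroll only mesh subjects or only native tissue subjects to reduce bias", but the same sentence goes on to offer centers with both arms as an alternative. Section 10.1 says only that subjects are "assigned to receive either the treatment or control procedure per site assignment", which fits either kind of center. No section gives the number of mixed centers. On center count, Section 8.1 says "The study will be conducted at up to 40 sites".

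**How the interval is built.** Section 12.2.3 opens with "Analyses comparing the treatment groups will be adjusted for the propensity score". It forms the difference within each propensity quintile, averages these with weights n_j/n to obtain D, and states that "D is approximately normally distributed with variance" V. Here V is the weighted sum of p(1-p)/n terms, or S²/n terms for continuous outcomes. Surgeon case volume is the only provider-level covariate listed for the propensity model.

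**Where V is used.** Section 12.1.1.3 uses it for the 95% effectiveness interval and the 90% safety interval, and Section 12.3.8.2 for the 90% interim intervals. Section 12.3.9 plans a poolability check of institutions within each group but states no consequence for the interval. No section adds a center component, a clustered variance or a design effect.

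**The concern.** V is a valid variance when subjects are independent given their propensity stratum. When a center contributes to one arm only, whatever its patients share (surgeon, technique, assessor, local reporting habits) does not cancel in D. It becomes part of the treatment contrast, and V leaves it out. Two conditions must both hold: center must determine arm, at least for many centers, and positive within-center correlation must remain after adjustment. The plan makes the first the default. It is silent on the second.

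If both hold, superiority and non-inferiority are claimed more often than the nominal rate. For safety, the error runs toward wrongly declaring mesh non-inferior on serious complications. The interim hypothesis tests are also meant to support a premarket approval application (Section 12.3.8.1, second footnote).

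**Working it through.** **1. The plan's own figures assume independence.**
- Effectiveness (85% vs 70%, two-sided 0.05, 90% power): n = (1.960+1.282)² × (0.85×0.15 + 0.70×0.30) / 0.15² = 157.6, stated 158 per arm.
- Safety (14% in both arms, margin 10%, one-sided 0.05, 80% power): n = (1.645+0.842)² × 2×0.14×0.86 / 0.10² = 148.9, stated 149 per arm.

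Both reproduce with no design effect.

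**2. Inputs.** From the documents: 330 evaluable subjects (8.1), 414 enrolled (12.1.1.2), and up to 40 sites (8.1). The safety denominator is the whole analysis population (12.1.1.3), so 414 for ITT. Assumed: ICC 0.005-0.05, 30-40 active centers of equal size, and the share f of subjects at centers that enroll 1:1.

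**3. Formulas.** With m subjects per center, the design effect is DE = (1-ICC) + ICC × m × (1-f). At f = 0 this is 1+(m-1)×ICC; at f = 1 it is 1-ICC. The one-sided error of the planned interval is 1-Φ(z/√DE), with z = 1.960 for superiority and 1.645 for safety and interim.
- Effectiveness: m = 330/40 = 8.25 to 330/30 = 11.
- Safety: m = 414/40 = 10.35 to 414/30 = 13.8.

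Example, 30 single-arm centers at ICC 0.02: DE = 1+10×0.02 = 1.20; 1.960/√1.20 = 1.789; error 3.7%.

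**4. Results, all centers single-arm.**

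| ICC | DE, effectiveness | Superiority error (nominal 2.5%) | DE, safety | False non-inferiority (nominal 5%) |
|---|---|---|---|---|
| 0.005-0.01 | 1.04-1.10 | 2.7%-3.1% | 1.05-1.13 | 5.4%-6.1% |
| 0.02 | 1.15-1.20 | 3.3%-3.7% | 1.19-1.26 | 6.6%-7.1% |
| 0.05 | 1.36-1.50 | 4.7%-5.5% | 1.47-1.64 | 8.7%-10.0% |

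Interim 90% interval, 330-414 evaluable (nominal 5%): 5.3%-6.1%, 6.2%-7.1% and 7.9%-10.0% for the same three rows.

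**5. Effect of mixing.** Half of centers mixed 1:1, at ICC 0.02 and 0.05: superiority 2.9%-3.0% and 3.4%-3.8%; safety 5.7%-6.0% and 6.7%-7.4%. All centers mixed 1:1: DE is 0.98 and 0.95, superiority error 2.4% and 2.2%, so no inflation.

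**6. Effect of unequal size.** Section 8.1 allows up to 50 subjects per site. With an assumed coefficient of variation of 0.6, m becomes m×(1+0.36). Single-arm superiority error is then 3.7%-4.2% at ICC 0.02 and 5.5%-6.6% at 0.05.

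**7. Simulation of the five-stratum interval** (beta-binomial center effects, equal single-arm centers; 6,000 replicates for superiority, 5,000 for safety at 24% vs 14%). Errors at ICC 0, 0.02 and 0.05:
- Superiority: 2.7%-2.9%, 3.7%-3.9%, 4.9%-5.6%.
- Safety: 5.3%, 6.5%-7.7%, 9.5%-10.4%.
- A center-clustered variance with a t reference, over all scenarios: 2.3%-3.2% and 4.9%-5.8%.

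With five imputations and about 20% missing (2,500 replicates), the planned superiority interval gave 2.8%-3.0%, 3.4%-3.6% and 4.3%-5.5%. Clustered variance combined by Rubin's rules gave 2.2%-2.7% throughout.

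**The case against.** **The size is unknown.** ICC, mixed share, active center count and the spread of shared Registry controls over sites are all missing, and all single-arm is the worst case for mixing. This stands. At ICC 0.005-0.01 the formula error (2.7%-3.1%) overlaps what the planned interval shows in simulation at ICC 0 (2.7%-2.9%), so a clustered variance brings no visible gain there.

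**Estimating the propensity score can make V conservative.** This also stands in part. A simulation with 13 estimated covariates (40 equal single-arm centers, 330 subjects, no confounding, 3,000 replicates) gave these superiority errors at ICC 0, 0.01 and 0.02:
- Covariates explaining about 23% of latent outcome variance: 1.8%, 2.6%, 2.6%.
- Explaining 10%: 2.4%, 3.1%, 3.5%.
- Not prognostic: 3.2%, 3.2%, 3.6%.

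Strongly prognostic covariates can therefore offset the effect at ICC 0.02 or below. At 0.05 the error stayed near 5% in every case.

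**The plan already limits center effects.** Procedures are standardized, surgeons are trained with a 10-procedure minimum, and surgeon case volume is in the propensity model. These may lower the ICC but add nothing to V. The poolability check in 12.3.9 looks in the right place but leaves the interval unchanged.

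**Stronger readings that a reader might infer.**
- That center fully determines arm. The Synopsis and Sections 8.2 and 12.2.2 all allow mixed centers.
- That sites may vary the surgery freely, or that surgeons routinely grade their own results. Section 8.2.1 allows only minor changes, and says so only in the mesh paragraph; in Section 8, surgeon POP-Q measurement is a fallback when no other trained provider is available.

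**Conclusion.** The point holds in conditional form. V has no center component, single-arm centers are the rule in 12.2.2 and the default in 8.2, and nothing else in the plan corrects the interval. To the extent that center determines arm and positive correlation remains, the co-primary and interim intervals are too narrow.

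On the assumptions above, the excess error is small at ICC 0.01 or below and may be offset altogether at 0.02 or below. At ICC 0.05 with all centers single-arm, superiority error is roughly double its nominal rate (4.7%-5.5% against 2.5%), and safety error is 8.7%-10.0% against 5%. Mixed centers lower these figures and unequal center sizes raise them. The documents do not support a claim that the intervals are wrong by any particular amount. They show only that the plan does not guard against this error, and that the guard is cheap.

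**What to change.** Keep D. For both co-primary endpoints and the interim tests, replace V with a center-clustered (linearised sandwich) variance: sum each center's contributions to D, square, and add over centers. Use a t reference with about (centers - 2) degrees of freedom. A center-level bootstrap that re-estimates the propensity score and quintiles in each resample is an alternative. For effectiveness, compute the clustered variance in each imputed data set and combine by Rubin's rules.

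If V stays primary, prespecify the clustered interval as a sensitivity analysis and state which governs if they disagree. In either case:
- report the observed ICC and the numbers of single-arm and mixed centers;
- state in 12.1.1.2 that the power figures assume no center correlation;
- for shared controls, use the Registry site as the cluster where it is available, and otherwise report results with and without them.

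Extending this to the secondary comparisons and the tests in 12.3.5.2 is optional.

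**Cost.** SAP wording, programming and a site identifier for every subject; the documents do not say whether Registry controls carry one. No new patients are needed, and enrollment ended in December 2016, so N cannot change. With single-arm centers the 95% interval widens by the factor (t/1.960)×√DE, with t = 2.024 (38 df) or 2.048 (28 df): 3%-4.5% at ICC 0, 10%-15% at 0.02 and 21%-28% at 0.05. Effectiveness power at 165 per arm becomes about 84%-86% at ICC 0.02 and 75%-79% at 0.05 (stated 90%). Safety power at 207 per arm becomes 82%-84% and 72%-77% (stated 80%).

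The change corrects the error bars only. Confounding of arm with center remains.
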